Historically, demodex blepharitis and MGD were treated together using mechanical treatment like warm compression and lid scrubbing and pharmacological treatment as Tea Tree Oil (TTO)(4). An FDA-approved solution for the disease is lotilaner ophthalmic solution, 0.25% (5), but its high cost at 1,957 USD per 10 ml is a notable drawback.

Hyun et al. (2012) found that only 7% of patients were Demodex-free after eyelid scrubs without the use of TTO. Therefore, in practice, we now recommend that patients with Demodex blepharitis treat their condition with eyelid scrubs containing TTO for higher treatment efficacy.(6)

Patients often find eyelid hygiene tedious and time-consuming, leading to poor treatment compliance (7). Recent innovations in in-office MGD management include Intense Pulsed Light (IPL), proposed as an adjunctive therapy for demodicosis. IPL's heat transfer may kill Demodex mites and soften meibum, reducing inflammatory mediators. Limitations include cost and inapplicability to patients with darker skin tones (Fitzpatrick V or VI), light-intolerant individuals, or pediatric patients (4).

An alternative cellular-level therapy overcoming IPL limitations is Low-Level Light Therapy (LLLT), using near-infrared light to induce mitochondrial light absorption and cell photoactivation, causing changes in inflammatory protein expression (8). This technology, recognized by NASA for

plant growth and astronaut wound healing (9), has diverse applications, including dermatology for Androgenetic Alopecia (AGA), skin rejuvenation, body contouring (10), and orthopedics for reducing edema, inflammation, and relieving pain and stiffness.

For direct effect to demodex mite Avci et al. (2013) and Sulek et al found that blue light activates porphyrins, leading to an antibacterial effect(11, 12). Rhee et al. (2023) conducted a comprehensive review revealing that Demodex mites can carry Streptococcus and Staphylococcus species on their surface, while *Bacillus oleronius* is present in their abdomen.(4)

Recently, LLLT has been used for MGD, with devices allowing combined (13) or separate (14) treatment with IPL or LLLT emerging as alternatives for MGD management.

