For our study, we will exclude patients with moderate and poor compliance. By focusing on patients who strictly adhere to the treatment protocol, we aim to more accurately assess the effectiveness of the intervention.

4.5) FDA approved medication for Demodex blepharitis : Lotilaner ophthalmic solution 0.25% is the only medication for Demodex blepharitis that was FDA-approved in July 2023(5). A recent meta-analysis showed that lotilaner significantly reduces Demodex mite density and mean collarette scores compared to a placebo(24). However, the cost per bottle is \$2,031 for 10 milliliters, and it is not available in Thailand. Consequently, we did not select this medication as an intervention in our study.

4.6) Several imaging modalities are used to diagnose MGD, with meibography emerging as a key tool for evaluating the structure and function of the meibomian glands. Traditional meibography employs infrared light to visualize gland architecture and assess gland dropout, but its reliance on manual interpretation can introduce subjectivity. The advent of artificial intelligence

(AI) in ophthalmology has opened new opportunities for more precise, automated, and objective assessments of meibomian gland health. AI-assisted meibography systems, particularly those based on deep learning algorithms, offer the potential to enhance the accuracy of MGD diagnosis and monitoring by providing automated segmentation, analysis, and grading of meibomian glands(25)

Recent studies have demonstrated the effectiveness of AI in analyzing meibography images to detect structural changes in the glands, including gland dropout and atrophy, with high sensitivity and specificity. [name] et al. described the use of deep learning models in meibography for the automatic segmentation of meibomian glands, offering a significant improvement over manual grading in terms of both speed and consistency. Their software integrates multiple steps, including image normalization, automatic segmentation, and manual refinement, to ensure high-quality analysis (18) By providing quantitative data on gland morphology, AI-based tools can assist clinicians in more accurately diagnosing MGD and tailoring treatment plans (26)

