Alternative Hypothesis (H1):

There is a significant difference in the reduction of Demodex mite count among patients with Demodex Blepharitis treated with at least one of the following therapies: Low Level Light Therapy (LLLT), Intense Pulse Light Therapy (IPL), Combined LLLT + IPL, greater than Mechanical with pharmacological Treatment.

[figure not shown]
Hypotheses

- LLLT or IPL, will be equally effective in reducing Demodex mite count and improving ocular surface parameters.
- IPL + LLLT will be more effective than LLLT or IPL alone in reducing Demodex mite count and improving ocular surface parameters.

7. Keywords

Demodex blepharitis, MGD, LLLT, IPL, Demodex mite count, Demodex mite eradication, Ocular surface parameters

Conceptual framework

Variables

Independent variables:

the different treatment modalities:

- 1.Low Level Light Therapy (LLLT)
- 2.Intense Pulse Light Therapy (IPL)
- 3.Combined LLLT + IPL
- 4.Mechanical with pharmacological treatment

Dependent variables: Mean Demodex Count, MGD Staging, OSDI Questionnaire, Meibum Quality, Meibum Expressibility, Telangiectasia Grading (0-3), Surface Staining (NEI Grading System), % Meibomian Gland Loss (MGL), Lipid Layer Thickness, Noninvasive Break-Up Time (NIBUT), Tear Meniscus Height (TMH),

8. Research Design

Single Center, 2x2 Factorial Randomized Control Trials

9. Research Methodology

Target Population: Demodex blepharitis patients at the Department of Ophthalmology, King Chulalongkorn Memorial Hospital.

This is a single-center, prospective, 2x2 factorial Randomized Control Trials involving outpatients with Demodex blepharitis presenting at the Department of Ophthalmology, King Chulalongkorn Memorial Hospital (KCMH) from Nov 2024 to Nov 2025.

The approach to participants: involves patients under the care of the research physician. They are recruited through advertisements and contacted through the patient's physician to introduce the researcher and seek volunteer participation.

The inclusion criteria consist of:

1. All patients who received a definite diagnosis of demodex blepharitis based on cylindrical dandruff at the base of the lashes and the presence of at least one alive demodex mites on eyelid margin by microscopy
2. Age >18 years.
3. Patients who can understand and follow the study instructions and can adhere to the scheduled follow-up plan.

The exclusion criteria consist of:

1. Patients who received previous treatment IPL or LLLT

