2. Poor compliance with eyelid scrubbing using tea tree oil (TTO)
3. Dead demodex mite on lash.
4. Contraindication of IPL: Skin Fitzpatrick scale V/VI, patients with pigmented lesions on the treatment area (Eyelid, Cheek).
5. Pregnancy or breastfeeding.
6. Active Skin disease: facial skin cancer, graft-versus-host disease, systemic lupus erythaematosus
7. Active eye infection: recurrent herpes simplex
8. Other lid disease ocular trauma, ocular deformity scar, exophthalmos, eyelid insufficiency
9. Patients with pigmented lesion on area of treatment.

We will use computer-generated random number allocation into 4 groups in a 1:1:1:1 ratio including seed number, with the outcome assessor blind and participant blind with allocation concealment:

- 1.) ShamLLLT + ShamIPL
- 2.) LLLT + ShamIPL
- 3.) IPL + ShamLLLT
- 4.) LLLT + IPL

***All groups receive mechanical with pharmacological treatment (Warm compression + Lid hygiene + 1% TTO) for 90 days with google form logbook for record compliance and prevent co-interventional treatments.

***All group with participant/investigator/interpreter blind.

Blinding and Allocation Concealment in Research Team:

1st Research Assistant : Allocates patients according to computer-generated random number allocation, ensuring allocation concealment, Evaluated VA , IOP , OSDI score by reads the questionnaire to the participant

2nd Research Assistant (The treatment administrator) : Administers IPL, LLLT, or sham treatments.

3rd Research Assistant : Conducts assessments using Keratograph and Lipiview2.

Main Researcher : Evaluates primary and secondary outcomes using case record forms, remaining blind to the treatment groups.

Intervention Description

Mechanical with pharmacological treatment : Warm compression 15 minutes + Lid hygiene + 1% TTO for 90 days

1%TTO : OCuSOFT Oust Demodex Eyelid Cleanser Foam Bottle 50ml (OCuSOFT, Richmond, TX) is the only commercially available medication in Thailand that contains 1% tea tree oil.

IPL : The Eye-light device (Espansione Marketing S.p.A., Bologna, Italy, waveleggths 1,200-1,500 nm, Delivery system 12cm²) (Thai FDA No 66-2-2-0012685) :

- Protective eye shields
- 5 flashes of light were applied for each eye (3 along the inferior orbital rim, 1 at the lateral canthus, and 1 applied horizontally along the inferior orbital rim)
- Therapeutic energy level (10–16 joules/ cm²) based on the degree of skin pigmentation.

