Patients will benefit from receiving treatment for Demodex Blepharitis through eyelid scrubbing + 1% TTO (tea tree oil) and eyelid scrubbing + Low-Level Blue Light Therapy (LLLT) + Intense Pulsed Light (IPL) performed by specialized ophthalmologists. Volunteers will not receive any other benefits from participating in the research. All trial procedures will be tested by researchers and the team beforehand to identify potential issues. Safety will be paramount during the experiment, with basic first aid procedures in place and guidelines for referring participants in case of injuries or adverse effects

Justice:

Equitable Participant Selection: Justice demands fairness in participant selection, avoiding bias or discrimination. All eligible individuals should have an equal opportunity to participate, promoting inclusivity.

Researchers design the recruitment process to ensure diversity and representation across various demographics. The selection criteria based on scientific relevance, fostering inclusivity in the study population.

This research has clear inclusion and exclusion criteria, equally distributes risks and benefits, and employs a stratified study group allocation method.

Equitable Access to Benefits: The principle of justice extends to ensuring that the benefits resulting from the study are accessible to a broad population, preventing disparities in access to potential interventions.

Researchers proactively consider the implications of the study outcomes and work towards facilitating equal access to any effective interventions emerging from the trial, minimizing healthcare disparities.

Outcomes

Primary Outcome: Mean of Demodex Count - the number of Demodex mites per eyelash on a total of 4 collarettes lashes epilation per one eye in 30 days after end of treatment.

Secondary Outcomes:

- Mean of Demodex Count - the number of Demodex mites per eyelash on a total of 4 collarettes lashes epilation per one eye in 90 days after end of treatment.
- MGD Stage 1-5.

OSDI questionnaire used to evaluate ocular dry eye symptoms.

Meibum Quality.

Meibum Expressibility.

Telangiectasia grading: 0-3

- Surface Staining: NEI Grading System.
- LIPIMIEW used to measure Lipid Layer Thickness.
- The Keratograph 5M (OCULUS, Germany) used to measure noninvasive break-up time (NIBUT), tear meniscus height (TMH), % Meibomian Gland Loss (MGL)

13. Expected or Anticipated Benefit Gain

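### Tea tree oil (TTO) use before entry has no eligibility rule, no listed baseline item and no place in randomisation or analysis, although every arm receives TTO

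*Combined protocol and SAP*

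**What the plan says.** **Eligibility.** Section 9, exclusion 1, covers "Patients who received previous treatment IPL or LLLT" and no other earlier treatment. Exclusion 2 is the only criterion that names TTO: "Poor compliance with eyelid scrubbing using tea tree oil (TTO". Section 4.4 is wider: "For our study, we will exclude patients with moderate and poor compliance". Neither says whether compliance is judged at screening or during the trial, and neither sets a rule on having used TTO. Inclusion needs cylindrical dandruff and at least one live mite.

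**Likely source of prior users.** The background says that "in practice, we now recommend that patients with Demodex blepharitis treat their condition with eyelid scrubs containing TTO for higher treatment efficacy". Under Section 9 the approach to participants "involves patients under the care of the research physician", and advertisements are also used.

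**Treatment.** "All groups receive mechanical with pharmacological treatment (Warm compression + Lid hygiene + 1% TTO) for 90 days" (Section 9).

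**Baseline data.** Sections 9 and 10 list acuity, pressure, OSDI, mite count, lid and meibum signs and imaging, but no treatment history. The logbook covers compliance and co-intervention during the study.

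**Allocation and analysis.** Section 9 describes a computer-generated 1:1:1:1 allocation with no factor. Section 12 (Justice) says the study "employs a stratified study group allocation method" and also names no factor. Section 11 gives ANOVA and chi-square tests without covariates. It does not name the mite count in the analysis paragraph, though the sample size rests on one-way ANOVA with pairwise comparisons.

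**The concern.** The hypotheses in Section 6 are about reduction in mite count. Section 4.4 cites evidence that good compliance with TTO scrubs lowers that count. For a patient new to TTO, the fall by week 8 includes the effect of starting it. For a patient who still has live mites despite using TTO, most of that effect may already have occurred. Both can enter, and the plan as written does not tell them apart.

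Two things are at stake. The first is precision: a prognostic difference left in the error term, and small arms that can differ in it by chance. The second is interpretation: readers could not say whether light was tested as an addition to newly started TTO or in patients whose mites had persisted on it. A history not taken at entry is hard to recover later.

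**Working it through.** The plan gives no figure on prior TTO use, so there is none to reproduce. The check asks how large the effect could be.

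**Inputs from Section 11:** 22 per arm, hence 44 v 44 for a factorial main effect; SD 3.56 (a baseline-count SD from a cited study); target difference 3.18 − 1.59 = 1.59.

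**Assumed:** share of prior users p = 0.5, with range 0.2 to 0.7; difference in mean reduction between TTO-naive patients and prior users g = 1.59 mites per lash, borrowed from the target only as a scale.

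1. *Chance difference in the share of prior users between two groups of n*: SD = sqrt(2p(1 − p)/n).
   - n = 22, p = 0.5: sqrt(2 × 0.25/22) = 0.151, or 15 points; 1.96 × 0.151 = 0.295, or about 30 points.
   - n = 44, p = 0.5: sqrt(2 × 0.25/44) = 0.107, or 11 points.
   - n = 22, p = 0.2: sqrt(2 × 0.16/22) = 0.121; p = 0.7: sqrt(2 × 0.21/22) = 0.138. So p = 0.5 is the least favourable case.

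2. *Shift in the contrast* = imbalance × g.
   - 22 v 22, one SD: 0.151 × 1.59 = 0.24; at 1.96 SD: 0.295 × 1.59 = 0.47.
   - 44 v 44, one SD: 0.107 × 1.59 = 0.17.
   - 22 v 22 with p = 0.2: 0.121 × 1.59 = 0.19. With p = 0.5 and g halved to 0.795: 0.151 × 0.795 = 0.12.

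3. *Compared with the noise*: SE = SD × sqrt(2/n).
   - 22 v 22: 3.56 × sqrt(2/22) = 1.07, so 0.24/1.07 = 0.22 SE and 0.47/1.07 = 0.44 SE.
   - 44 v 44: 3.56 × sqrt(2/44) = 0.76, so 0.17/0.76 = 0.22 SE.

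4. *Precision gained by removing it*: variance due to prior use = p(1 − p)g² = 0.25 × 1.59² = 0.63.
   - Total variance 3.56² = 12.67; share 0.63/12.67 = 5%; sqrt(1 − 0.05) = 0.975, so the SE narrows by about 2.5%. This is worth about 0.05 × 22 = 1.1 patients per arm.
   - If the outcome SD before adjusting for prior use were 2 (assumed): 0.63/4 = 16%; sqrt(1 − 0.16) = 0.92, so the SE narrows by about 8%.

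5. *How often a visible imbalance arises* under simple randomisation with 22 per arm, for p from 0.2 to 0.7. A given pair of arms differs by 20 points or more with probability 9% to 17% (exact binomial). The widest gap among the four arms reaches 20 points with probability 32% to 53% (simulation, 400,000 draws). For 44 v 44 the probability is 2% to 7%.

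**The case against.** The case against giving this weight is strong on size. Every arm gets the same TTO and patients are randomised. Chance imbalance in a prognostic factor is therefore ordinary sampling error, already counted in the standard error. A shift of 0.22 SE is small. The visit-1 mite count is already measured and may absorb much of any difference due to earlier treatment. A mixed population is a legitimate choice for an add-on trial. All of this stands.

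Four stronger readings are tempting, and the documents do not support them.

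- *That many patients will arrive already on TTO.* No rate is given. The background sentence follows from a cited study and does not describe this clinic's caseload. Recruitment is also by advertisement, and newly diagnosed, untreated patients fit the text equally well.
- *That prior use is not recorded at all.* The case record form was not supplied, and Section 11 promises baseline clinical characteristics without itemising them. What can be said is that prior use is not listed.
- *That TTO is ignored in eligibility.* Exclusion 2 and Section 4.4 address it, but through adherence. Applied at screening, exclusion 2 would need a TTO history and would keep patients who had used it well. Applied during the trial, it says nothing about earlier use. The dead-mite exclusion may filter some treated patients, but it is not a history rule.
- *That a stratified list alone would cure the imbalance.* Simple randomisation within strata leaves the same chance imbalance. Restriction, such as blocks, is needed.

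The objection does not answer the gap in interpretation, the undefined timing of exclusion 2, or the two descriptions of allocation.

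**Conclusion.** The point holds as a minor one. The plan has no rule on exposure to TTO before entry, does not list it at baseline, and does not use it in randomisation or analysis. Its only TTO criterion is about adherence and has no stated timing.

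A reader might infer that the estimated light effect is biased. It is not biased on this account, because arms are randomised and share the same TTO regimen. The cost is modest variance, possible chance imbalance and an unclear target population.

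With half prior users and a 1.59-mite difference, both assumed, a one-SD imbalance moves a 22 v 22 contrast by 0.24 and a 44 v 44 contrast by 0.17, about 0.22 SE each at SD 3.56. The recoverable precision is about 2.5% of the SE, or about 8% if the SD were 2. Lower prior use or a smaller difference reduces these figures. Interpretability, more than precision, justifies acting.

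**What to change.** 1. Add a visit-1 item on prior TTO scrub use: none, past or current, with duration. State beforehand the cut-off that defines recent use.
2. Include prior use and the baseline mite count as covariates in the week-8 mite-count model. Show LLLT and IPL effects by prior use descriptively only.
3. Reconcile the stratified allocation in Section 12 with the unstratified description in Section 9. If randomisation has not started and prior TTO is chosen as the factor, use permuted blocks within the two strata. If it has started, take prior use from the charts and adjust for it.
4. State when exclusion 2 applies, and reconcile it with Section 4.4, which also removes moderate compliers. The clinical rule itself is for the sponsor.

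The cost is one baseline question, minor administration of the list, and one or two degrees of freedom. No treatment changes. Chart abstraction after the start may be incomplete, so recording at visit 1 is preferable.

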LLLT : The blue MY MASK-E (Espansione Marketing S.p.A., Bologna, Italy) (Thai FDA No 66-2-2-0012685)

- No eye shields
- Applying a special mask for 15 minutes, once a week for 4 weeks

ShamLLT : the MY MASK-E (Espansione Marketing S.p.A., Bologna, Italy) – No eye shields, applying a power off special mask for 15 minutes , once a week for 4 weeks

ShamIPL : the Eye-light device (Espansione Marketing S.p.A., Bologna, Italy) - Protective eye shields, 5 time for each eye with flashes of light off.

Epilation Strategies

the Modified Coston method as outlined by Gao et al. in 2005. In this method, two lashes containing cylindrical dandruff (CD) then additional **rotated around itself** were extracted from each eyelid of every participant using fine forceps. These lashes were then individually placed at opposite ends of a glass slide for observation under a slit-lamp biomicroscope (SL220; Carl Zeiss, Oberkochen, Germany) at a magnification of $\times 25$. This process resulted in four lashes of right eye being prepared across two slides for each participant. A coverslip was applied to each lash, followed by the slow pipetting of 20 μL of saline at the coverslip's edge until it surrounded the lash. Subsequently, 20 μL of 100% alcohol was pipetted at the same edge, extending the counting period for up to 20 minutes to facilitate the migration of embedded Demodex from the CD. The Demodex count was performed thrice under the microscope, and all samples were photographed using standard procedures by the same specialist. The presence of Demodex in at least one of the eight eyelashes was considered Demodex-positive

10. Data Collection:

Primary Outcome:

Mean of Demodex Count - the number of Demodex mites per eyelash on a total of 4 collarettes lashes epilation (2 from upper eyelid ,2 from lower eyelid and identification by anatomical imaginary line of nasal and temporal limbus) per right eye in 30 days after end of treatment. (8th week)

Secondary Outcomes:

1.Mean of Demodex Count - per right eye in 90 days after end of treatment.(16th week)

2.MGD staging (Severity)

[figure not shown]
OSDI questionnaire used to evaluate ocular dry eye symptoms.

OCULAR SURFACE DISEASE INDEX®					
Please answer the following questions by checking the box that best represents your answer.					
Have you experienced any of the following during the last week:					

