This research marks a pioneering and robust investigation into demodex blepharitis globally, utilizing a meticulously designed study approach tailored to the Thai population.

Aims to unveil unprecedented insights into the new less invasive, less session, better compliance optimal treatment modalities for demodex blepharitis. The expected benefits, applications, and utilization of the study findings are multifaceted, offering valuable contributions to both the scientific community and clinical practice.

Contributes to the optimization of light base treatment strategies for demodex blepharitis, helping clinicians tailor interventions based on their relative efficacy.

Provides a foundation for further research on the sustained effects of these interventions and informs the development of extended treatment protocols.

Generates new knowledge that extends beyond demodex mite eradication, encompassing the broader landscape of ocular surface health, ethical considerations in clinical trials, and the application of innovative therapeutic modalities. This knowledge contributes to the ongoing evolution of demodex blepharitis and meibomian gland dysfunction management and sets the stage for further advancements in ocular surface research.

14. Challenges and Limitations

1. Limited Generalizability

- Population Specificity: The study's focus on the Thai population may limit the generalizability of findings to broader demographic groups, making it challenging to apply results to populations with different genetic, environmental, and cultural backgrounds.

2. Long-Term Effects and Follow-Up

- Sustainability and Longevity: The relatively short follow-up period (90 days) may restrict the ability to capture long-term effects of the interventions. Extended longitudinal studies are necessary to assess treatment sustainability over time.

3. Blinding Constraints

- Blinding in Light-Based Interventions: Achieving complete blinding in light-based interventions (IPL and LLLT) is challenging, potentially introducing bias. The visible nature of these treatments makes it difficult to conceal allocation from both participants and investigators.

4. Outcome Measure Subjectivity

- Subjective Assessments: Reliance on patient-reported symptoms may introduce variability in study outcomes. While objective measures, such as Demodex mite count, offer a more standardized evaluation, they remain subject to interpretation.

5. Adherence and Compliance

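### Section 9 states participant blinding without qualification, but the unlit and non-flashing shams and the plan's own section 14 leave it not assured, which exposes the OSDI

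*Combined protocol and SAP*

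**What the plan says.** Section 9 makes the masking claim twice. The randomisation paragraph describes allocation "with the outcome assessor blind and participant blind with allocation concealment", and the note under the four arms adds "All group with participant/investigator/interpreter blind". Neither statement is limited to particular outcomes or people.

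The Intervention Description in section 9 defines what participants receive. Active LLLT is the blue mask, listed with no eye shields: "Applying a special mask for 15 minutes, once a week for 4 weeks". Its sham uses the same make of mask, again with no eye shields: "applying a power off special mask for 15 minutes". For active IPL, with eye shields, "5 flashes of light were applied for each eye". Sham IPL is "Protective eye shields, 5 time for each eye with flashes of light off".

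Section 14, item 3 (Blinding Constraints), then says: "The visible nature of these treatments makes it difficult to conceal allocation from both participants and investigators".

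Section 9 also sets out the team's roles. The 1st Research Assistant allocates patients and reads the OSDI to them. The 2nd delivers active or sham treatment. The 3rd runs the Keratograph and LipiView. The Main Researcher evaluates the primary and secondary outcomes and is stated to be blind.

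**The concern.** A reader of section 9 would take every between-arm difference as a blinded result. Section 14 says that this may not be so, but the caveat is not carried back to section 9, to the outcome list in section 10 or to the analysis in section 11.

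This matters most for the OSDI, where the participant's own answer is the measurement. If participants can tell which devices were switched on, a difference in OSDI can reflect expectation as well as treatment. Masking whoever later handles the case record form does not undo that.

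**Working it through.** The documents give no figure from which a bias could be calculated, such as a rate of correct guesses or an expectation effect on the OSDI. The check is therefore a comparison of passages, with one count.

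1. **LLLT cue.** Active and sham share the mask, the 15 minutes, the weekly schedule and the absence of eye shields. They differ in whether the mask is lit. The background text describes LLLT in general as near-infrared, but the device named in section 9 is the blue mask, sections 4.2 and 12 call the treatment blue light, and section 14 calls these treatments visible. The cue is therefore one a participant can plausibly see, at each of four sessions.

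2. **IPL cue.** Both conditions use eye shields and five applications per eye, so sight of the flash is limited. No substitute for the sound, warmth or sensation of a flash is described. The cue is weaker than for LLLT, but it is not removed.

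3. **How the cue lines up with the comparisons.** The arms are (1) both sham, (2) LLLT + sham IPL, (3) IPL + sham LLLT, (4) both active.
   - The unlit mask is worn in arms 1 and 3: 2 × 22 = 44 of 4 × 22 = 88 planned participants.
   - At least one switched-off device is used in arms 1, 2 and 3: 3 × 22 = 66 of 88.
   - Lit versus unlit coincides exactly with the LLLT factor. Four of the six pairwise comparisons differ in mask state (1–2, 1–4, 2–3, 3–4), and the other two (1–3, 2–4) differ in IPL state. No comparison is free of a possible cue.

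4. **What participants know beforehand.** Section 12 says that consent will cover randomisation and the details of each intervention. Section 15, item 2 requires possible discomfort from LLLT and IPL to be explained. Participants with no earlier light therapy will still have some idea of what an active session involves.

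5. **Who collects the OSDI.** The person who allocates and the person who reads the OSDI aloud are the same (1st Research Assistant). The plan does not say whether allocation is done without seeing the arm, so this person's masking is not established.

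6. **Whether MGD stage is exposed.** Figure 1 has rows for symptoms and for OSDI range beside rows for gland grade and meibum quality. Sections 10 and 12 list the OSDI directly below MGD staging. Section 10, item 7 also has MGD staging assessed from masked meibography images by an AI-assisted program. Images cannot supply the symptom and OSDI rows, and the readable text gives no rule for combining rows. The stage is exposed only as far as those two rows are used.

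7. **Checks planned.** Section 11 contains no assessment of masking and no statement on how incompletely masked outcomes will be read.

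**The case against.** The strongest reply is that section 9 states the intended procedure and section 14 honestly discloses its residual limit. Section 14 says that full blinding is challenging, not that there is none. The safeguards are real: every participant is exposed to both devices, the shams use the same equipment with matching mask time and number of applications, both IPL conditions are shielded, and section 9 excludes anyone previously treated with IPL or LLLT. The person who delivers treatment is separate from the Main Researcher.

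Much of this stands, and it rules out four stronger readings that a reader might infer:

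- *That the design has no participant masking.* The documents show masking that is weak and untested, not absent.
- *That the Main Researcher is unblinded.* Section 14's general sentence mentions investigators, but no route to this person is described, and the roles in section 9 are separated.
- *That MGD stage necessarily carries the bias.* This depends on an unstated combination rule.
- *That the primary mite count is biased because participants who guess sham change their scrubbing.* Section 4.4 cites a study linking compliance to mite count, so the path is conceivable. Nothing in the documents shows that it occurs, and the count is evaluated by a researcher stated to be blind.

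What does not stand is the idea that disclosure in section 14 settles the matter. Section 9 still makes an unqualified claim, and that is the section from which a report's masking description would be drawn.

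**Conclusion.** The participant-blinding statement in section 9 is wrong as written and must be reconciled with section 14. Participant masking is not assured, most clearly for LLLT. The OSDI is directly exposed, and its collector is not shown to be masked. MGD stage is exposed conditionally.

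The size of any bias cannot be estimated from the documents. What can be stated is its reach: half the planned sample wears an unlit mask, and all six pairwise comparisons differ in at least one device state. The conclusion assumes that the lit blue mask is perceptible to someone wearing it without shields, which section 14 supports, and that no undescribed sham feature imitates light, sound or warmth.

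The point should be corrected because it changes what can be concluded from the OSDI. It does not undermine the mite count, provided that the Main Researcher stays masked.

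**What to change.** 1. Reword section 9 to describe the trial as sham-controlled, with the Main Researcher masked for the mite count and participant masking not assured. A blanket label of outcome-assessor masked would not do, because it is not established for the OSDI. Align section 14 with the new wording.
2. Have the OSDI self-completed, or read by existing staff with no access to the allocation, for example the 3rd Research Assistant if kept masked.
3. State in section 11 that the OSDI, and MGD stage where it uses the OSDI, will be interpreted as incompletely masked outcomes. Say which rows of Figure 1 assign the stage.
4. Report logged scrubbing and compliance exclusions by arm. The logbook already collects the data, and the comparison tests the scrubbing path instead of assuming it.

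An allocation-guess question is optional. If used, it should be asked early, after the first session. A guess taken only at week 8 would mix unblinding with perceived benefit.

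The cost is revised text, a small reassignment of tasks and a less favourable masking claim. No new device, visit or participant is needed.
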